### Sample Size Estimation

Because this is an extension study, the sample size will be determined by the number of patients who have completed a parent study (MVT-601-3101 or MVT-601-3102) and who are eligible and willing to participate in the extension study. It is estimated that approximately 800 patients (67% of the total of 1200 patients who will be randomized into the parent studies) will participate in this study.

## 1.1. Schedule of Activities

**Table 1-1 Schedule of Activities for Study MVT-601-3103**

VISIT NAME (Timing is relative to MVT-601-3101/-3102)	PERIOD											SAFETY FOLLOW-UP
	Week 24/Baseline (Week 24 of Parent Study; Baseline of Extension Study)	Week 28 and Week 32	Week 36	Week 40 and Week 44	Week 48	Week 52 a	Week 65	Week 78	Week 91	Week 104 a / Early Termination	Un- scheduled b	Follow-Up c (~30 days after last dose of study drug)
Visit Window (days)	Parent Study Day 169 -10/+20	±7	±7	±7	±7	±7	±7	±7	±7	±7	-	-3 to +18
Informed Consent	X d											
Review Eligibility Criteria	X											
Concomitant Medications e	X f	X	X	X	X	X	X	X	X	X	X	X
Vital Signs (BP, HR, Temperature)	X g	X	X	X	X	X	X	X	X	X	X h	X
Weight	X g		X			X		X		X	X h	
Complete Physical Examination	X g					X i				X j	X h	
Visual Acuity k	X g											
Signs and Symptoms- Directed Physical Examination l		X	X	X	X		X	X	X		X h	X
12-Lead ECG m	X g					X				X h	X h	
Clinical Laboratory Tests n	X g,o	X	X	X	X	X n	X	X	X	X n	X h	X ee

	PERIOD											SAFETY FOLLOW-UP
VISIT NAME (Timing is relative to MVT-601-3101/-3102)	Week 24/Baseline (Week 24 of Parent Study; Baseline of Extension Study)	Week 28 and Week 32	Week 36	Week 40 and Week 44	Week 48	Week 52 a	Week 65	Week 78	Week 91	Week 104 a / Early Termination	Un-scheduled b	Follow-Up c (~30 days after last dose of study drug)
Visit Window (days)	Parent Study Day 169 -10/+20	±7	±7	±7	±7	±7	±7	±7	±7	±7	-	-3 to +18
Pharmacodynamics Sample p	X g,n					X n				X n	X h,n	
Urinalysis	X g					X				X	X h	
Pregnancy Test (Urine)	X g	X	X	X	X	X	X	X	X	X	X h	X
Daily eDiary q	X g	X	X	X	X	X	X	X	X	X		X
Site Review of eDiary Data	X g	X	X	X	X	X	X	X	X	X	X h	X
Bone Densitometry r	X g		X			X s,t				X r,s	X h	X ce
Endometrial Biopsy	X g,u					X				X t	X h	X ce
Dispense Study Treatment	X	X	X	X	X	X	X	X	X		X h	
Dispense or Prescribe Protocol-Specified Analgesic Drugs v	X	X	X	X	X	X	X	X	X		X h	
Treatment Compliance		X	X	X	X	X	X	X	X	X	X h	
Take Study Drug Dose in Clinic	X w					X				X	X h	
Daily Self-Administration of Study Treatment x		X ----- X										
Take Protocol-Specified Rescue Analgesics as Needed y		X ----- X										

VISIT NAME (Timing is relative to MVT-601-3101/-3102)	PERIOD											SAFETY FOLLOW-UP
	Week 24/Baseline (Week 24 of Parent Study; Baseline of Extension Study)	Week 28 and Week 32	Week 36	Week 40 and Week 44	Week 48	Week 52 a	Week 65	Week 78	Week 91	Week 104 a / Early Termination	Un- scheduled b	Follow-Up c (~30 days after last dose of study drug)
Visit Window (days)	Parent Study Day 169 -10/+20	±7	±7	±7	±7	±7	±7	±7	±7	±7	-	-3 to +18
EHP-30 Questionnaire z	X g		X		X	X		X		X	X h	
Patient Global Assessment for Pain y	X g	X	X	X	X	X	X	X	X	X	X h	
[on paper] Patient Global Assessment for Function aa	X g	X	X	X	X	X	X	X	X 	X	X h	
Patient Global Impression of Change y	X g		X			X					X h	
[on paper] EHP Work Domain z	X g					X		X		X	X h	
EQ-5D-5L Questionnaire y	X g					X		X		X	X h	
Adverse Event Collection bb	X	X	X	X	X	X	X	X	X	X	X	X
Status of Menstruation Recovery												X cc,cc
Telephone Contact dd						X (W57)	X (W71)	X (W85)	X (W98)			
Mammogram dd						X dd				X dd	X dd	

BP = blood pressure; DXA = dual-energy x-ray absorptiometry; ECG = electrocardiogram; eDiary = electronic diary; EHP = Endometriosis Health Profile; EQ-5D-5L = European Quality of Life Five-Dimension Five-Level Scale; HR = heart rate; NRS = Numerical Rating Scale; PGA = Patient Global Assessment; sB&B = Subject Modified Biberoglu and Behrman; W = week.

a The Week 52 visit should occur on or after the 1-year anniversary of Baseline Day 1 of the parent study (± 7 days), and the Week 104 visit should occur on or after the 2-year anniversary of Baseline Day 1 of the parent study.

b Unscheduled visits may be conducted at the investigator's discretion when needed. The reason for the visit will be captured in the source documents.

c The Follow-up visit may be waived if the patient enrolls directly into another relugolix clinical study upon completion of the Week 104 visit.

- d May be signed up to 30 days prior to the Week 24/Baseline visit or during the Week 24/Baseline visit. Enrollment in MVT-601-3103 is defined by administration of the first dose of MVT-601-3103 study drug.
- e Record all prescription and nonprescription drug and supplements taken from the Week 24/Baseline visit through the Safety Follow-Up Period. Concomitant medications with start date prior to the first dose of study drug for MVT-601-3103 should be reported as concomitant medications in the parent study (MVT-601-3101 or MVT-601-3102). If concomitant medication is ongoing at the time of the first dose of study drug for MVT-601-3103, please see the Case Report Form Completion Guidelines for instructions for recording the follow-up status.
- f Concomitant medications are recorded both for the parent study and for MVT-601-3103 at the Week 24/Baseline visit. (See footnote e for further details).
- g This is a parent study (MVT-601-3101 or MVT-601-3102) Week 24 procedure that serves as the Week 24/Baseline procedure for MVT-601-3103 and is covered under the informed consent for the parent study.
- h The indicated procedure may be performed at the Unscheduled visit based on the purpose of the visit (eg, follow-up for an adverse event or abnormal laboratory test).
- i The Week 52 and Week 104 physical examinations will include a breast examination.
- j See parent study protocols (MVT-601-3101 or MVT-601-3102) for instructions on testing visual acuity.
- k The examination may include a gynecologic examination, if indicated based on signs and symptoms.
- l The 12-lead ECGs will be submitted for central reading.
- m Clinical chemistries will be collected at each visit. A complete blood count will be collected at Week 24/Baseline, Week 28, Week 36, Week 52, Week 65, Week 78, Week 91, and Week 104. At the Week 24/Baseline visit, Week 52 visit, and Week 104 visit, additional tests will include the following: fasting (at least 8 hours) glucose, lipid profile, and hemoglobin A1c.
- n Samples should be obtained in a fasted state (at least 8 hours). Water is allowed during the fasting period.
- o For Week 24/Baseline samples, see the parent protocol (MVT-601-3101 or MVT-601-3102). At Week 104/Early Termination, collect a sample for analysis of estradiol concentrations only. On days when pharmacodynamics samples are collected, administer the study treatment after the pharmacodynamics sample collections are collected.
- p All women enrolled in the study will continue to use the patient eDiary dispensed in the parent study. Patients will complete daily eDiary entries, including NRS pain scores, menstruation information, analgesic drug use, date and time of study drug administration, and sB&B scale scores until Week 52. After Week 52, eDiary scores will be entered over four eDiary collection cycles on the following schedule: Week 57 to the Week 65 visit, Week 71 to the Week 78 visit, Week 85 to the Week 91 visit, and Week 98 to the Week 104 visit.
- q Bone densitometry (L1-L4, total hip, femoral neck) will be submitted for central reading.
- r See Section 6.5.2.6 for details on the timing and follow-up of bone densitometry.
- s Determination of bone mineral density by DXA at Early Termination and follow-up of findings will proceed based on the timing of the Early Termination visit. For Early Termination occurring after Week 24 and before Week 36, DXA is not required at Early Termination visit unless it will aid in the assessment of an adverse event, and follow-up DXA required at 6 months ( $\pm$  1 month) if most recent DXA bone mineral density loss at lumbar spine (L1-L4) or total hip was  $>$  2% relative to the parent study baseline. For Early Termination occurring after Week 36 and before Week 52, DXA is required at Early Termination unless a DXA result is available from within six weeks prior to Early Termination, and follow-up DXA is required at 6 months ( $\pm$  1 month) if the most recent DXA scan was at Week 24 and bone mineral density loss at the lumbar spine (L1-L4) or total hip was  $>$  2% or most recent DXA result was after Week 24 and bone mineral density loss at the lumbar spine (L1-L4) or total hip was  $>$  3%, relative to the parent study baseline. For Early Termination occurring between Week 52 and Week 104, DXA is required at Early Termination unless a DXA result is available from within six weeks prior to Early Termination, and follow-up DXA is required at 6 months ( $\pm$  1 month) if on the most recent DXA, bone mineral density loss at the lumbar spine (L1-L4) or total hip was  $>$  7%, relative to parent study baseline.

- t Endometrial biopsies are to be done per instructions in the parent study. Procedures for handling and shipping biopsy samples to the central laboratory for analysis are described in the Investigator Site File. An endometrial biopsy will have been performed at the parent study Week 24 visit for all patients who participated in MVT-601-3101 only (see MVT-601-3101 protocol for details) and at Week 52 and Early Termination visit for all patients. This procedure is not required at the Early Termination visit in patients whose last dose of study drug was taken during Week 32 or earlier or within four weeks after completion of the Week 52 endometrial biopsy. However, the procedure may be done if it will aid in the evaluation of an ongoing adverse event. An endometrial biopsy at Week 104 is recommended for all patients who complete the open-label extension; however, patients will have the option to opt out.
- u Please see Appendix 1 for list of protocol-specified analgesics and see the Investigator Site File for information on where and how to obtain protocol-specified analgesic medications by country. At the Week 104 visit, patients who will not be proceeding to another extension study will be re-dispensed or prescribed protocol-specified analgesic drugs, if needed, to ensure sufficient supply until the Follow-Up visit. For patients proceeding to another extension study, refer to the protocol for that next study.
- v Pregnancy test must be negative before the study drug dose is administered. For patients whose Baseline Day 1 visit is conducted on a different day than the parent study Week 24 visit, perform an unscheduled pregnancy test at Baseline Day 1 prior to administering the first dose of study drug.
- w Patients will take the first dose of the study drug for this study once daily starting with the Week 24/Baseline visit (taken at the visit). If necessary, for logistical reasons (eg, delayed availability of study drug supply on site, others), and with sponsor/designee approval, the first dose of open label study drug for MVT-601-3103 may be administered up to 10 days following the parent study Week 24/Baseline visit. If the first dose of study drug is not given during this up to 10-day interval, the parent study follow-up procedures should be followed (ie, adverse event reporting, eDiary completion, etc.). The first dose of study drug for this extension study must not be taken until all parent study Week 24 procedures such as laboratory tests have been completed. Therefore, results of testing required for eligibility (eg, DXA) must be available on or prior to the Week 24/Baseline visit. The last dose of study drug will be taken in the clinic during the Week 104/Early Termination visit.
- x Patients may only take their study-specified analgesics for pain. Analgesics should not be taken prophylactically (ie, in anticipation of pain).
- y The patient will enter her response(s) into an electronic tablet device at the site. On visits when both tablet and paper questionnaires are being performed at the site, the patient should complete the tablet questionnaires before the paper questionnaires.
- z The patient will enter her response onto a paper questionnaire at the site. Paper questionnaires should be done in the following order: PGA for function, EHP Work Domain.
- aa Collect adverse events from the time that the first dose of study drug for MVT-601-3103 is administered. Adverse events with onset prior to the first dose of study drug for MVT-601-3103 should be reported as an adverse event in the parent study (MVT-601-3101 or MVT-601-3102). If events originating in the parent study are ongoing at the time of the first dose of study drug for MVT-601-3103, please see the Case Report Form Completion Guidelines for instructions for recording the follow-up status.
- bb Patients whose menses have not resumed as of the Follow-up visit for whom there is no explanation for the lack of resumption (eg, medical procedure or medications) will be contacted by telephone 3 (+0.5) months after the Follow-Up visit to determine if menses has resumed and questioned about factors that may affect resumption of menses. If a patient is lost to follow-up, three documented attempts should be made to contact the patient by telephone. If unable to contact the patient by telephone, a certified letter must be sent to the patient.
- cc A telephone call will be performed at Weeks 57, 71, 85, and 98. The following activities should be completed: a concomitant medication review, evaluation of adverse events, and a review of eDiary and study medication compliance.
- dd For patients  $\geq 40$  years old at the time of the Week 52 visit, Week 104 visit, or Early Termination visit only. See Section 6.5.2.9.
- ee See Section 6.5.2.6, Section 6.5.2.7, and Section 6.5.2.8 to determine if additional follow-up is required.

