#### **4.5. Removal of Patients from Therapy**

Completion of the Week 104 visit defines completion of the study. Patients may withdraw consent to participate in the study and discontinue treatment at any time for any reason. Investigators or the medical monitor may remove patients from therapy under this protocol for reasons of safety and/or lack of compliance as discussed below. Patients removed from therapy for any reason will undergo the assessments for the Early Termination visit (see the Week 104 visit on the Schedule of Activities, Section 1.1) and will have a Follow-up visit to assess safety approximately 30 days after the end of study drug treatment (ie, after the patient's last dose of study medication). When patients complete the study or early terminate from the study, they must be deactivated from the study in the interactive voice response system/interactive web response system (IVRS/IWRS), eDiary, and tablet device.

The following safety and/or compliance events will result in the removal of patients from therapy either permanently or until the etiology of the problem has been identified and resolved:

- Any adverse event that is intolerable to the patient and that cannot be ameliorated by the use of adequate medical intervention, or that in the opinion of the investigator or medical monitor would lead to undue risk to the patient if dosing continued;
- If it is discovered after enrollment that a patient failed to meet protocol entry criteria and continued participation poses an unacceptable risk to the patient's health;
- If the following liver test abnormalities develop, study drug should be discontinued immediately with appropriate clinical follow-up (including repeat laboratory tests, until a patient's laboratory profile has returned to normal/baseline status):
  - ALT or AST > 8 x ULN; or
  - ALT or AST > 5 x ULN and persists for more than 2 weeks; or
  - ALT or AST > 3 x ULN in conjunction with elevated total bilirubin > 2 x ULN or international normalized ratio (INR) > 1.5; or
  - ALT or AST > 3 x ULN with appearance of fatigue, nausea, vomiting, right upper quadrant pain or tenderness, fever, rash and/or eosinophilia (> 5%);

- 
- QT interval by the Fridericia correction (QTcF) prolongation of more than 500 msec read by a cardiologist;
  - Evidence of endometrial hyperplasia or endometrial carcinoma on endometrial biopsy;

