### **5.4. Directions for Administration**

All study patients will take a study treatment of one tablet and one capsule once daily.

The study treatment should be taken in the fasted state (other than water, tea, or coffee) in the morning, at least 1 hour before breakfast. If dosing is missed in the morning for any reason, the study treatment may be taken later in the day, under fasting conditions, at least 1 hour before or 2 hours after eating a meal. The study treatment should be taken as close as possible to the same time of morning each day.

On Week 24/Baseline 1, Week 52, and Week 104 clinic visit days, study drug will be administered in the clinic rather than at home (see Schedule of Activities in Section 1.1).

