### **6.3. Early Termination Visit and Follow-up Visit**

All patients withdrawing from the study prior to Week 104 will complete an Early Termination visit. The Early Termination visit procedures are identical to those of Week 104. An endometrial biopsy is required for all patients at the Early Termination visit except for patients whose last dose of study drug was taken during Week 32 or earlier or within four weeks after completion of the Week 52 endometrial biopsy. However, the endometrial biopsy may be obtained if it will aid in the evaluation of an ongoing adverse event.. Bone densitometry may be performed at the investigator's discretion, if it aids in follow-up of an ongoing adverse event(s). Follow-up bone densitometry findings for patients who terminate from the study early will proceed according to the rules provided in Section 6.5.2.6.

Patients (including those who complete the Week 104 visit and those who withdraw early from this study) will have a Follow-up visit approximately 30 days after the last dose of study drug, or prior to the date of initiation of another investigational agent or hormonal therapy affecting the hypothalamic-pituitary-gonadal axis or surgical intervention or other invasive procedure for endometriosis, whichever occurs first. However, for patients who enroll directly into another relugolix clinical study upon completion of the Week 104 visit, the Follow-up visit may be waived.

The Follow-up visit will be used to assess safety after discontinuation of study treatment including adverse events, clinical safety laboratories, and return of menstruation. Refer to the Schedule of Activities (see Section 1.1) for individual study visit procedures during the Follow-up visit.

Follow-up of bone densitometry findings for patients who terminate from the study early will proceed according to the rules provided in Section 6.5.2.6.

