## **6.5. Study Procedures**

### **6.5.1. Efficacy-Related Procedures**

#### **6.5.1.1. Pharmacodynamics Sample Collection**

A blood sample for the pharmacodynamic analysis of serum estradiol will be collected predose at the visits indicated in the study Schedule of Activities (see Section 1.1), other than at the Week 104 or the Early Termination visit, when no dose is administered. These pharmacodynamic samples will be analyzed at a central laboratory. These results will not be shared with the sites at any time.

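### The Schedule and footnote w call for an in-clinic dose at Week 104/Early Termination, Section 6.5.1.1 says none is given, and no dosing exception is written for women already stopped for safety: a low-impact contradiction to correct

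*Protocol*

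**What the plan says.** Three places put a dose at the final visit.

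- Table 1-1 has a row headed "Take Study Drug Dose in Clinic". It is marked at Week 24/Baseline, Week 52, Week 104/Early Termination and Unscheduled. The Week 104/Early Termination mark carries no qualifying footnote.
- Footnote w: "The last dose of study drug will be taken in the clinic during the Week 104/Early Termination visit".
- Section 5.4, for Week 104 only: "On Week 24/Baseline 1, Week 52, and Week 104 clinic visit days, study drug will be administered in the clinic rather than at home". Early Termination is not named.

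One place says the opposite. Section 6.5.1.1 requires the estradiol sample to be predose, "other than at the Week 104 or the Early Termination visit, when no dose is administered".

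Two further sections decide who meets these instructions. Section 6.3 says: "The Early Termination visit procedures are identical to those of Week 104". It then adds qualifications for the endometrial biopsy and bone densitometry, and none for dosing. Section 4.5 says: "Patients removed from therapy for any reason will undergo the assessments for the Early Termination visit". The reasons for removal in that section include safety stops, and for one of them the wording is explicit: "If the following liver test abnormalities develop, study drug should be discontinued immediately with appropriate clinical follow-up".

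**The concern.** A site that follows the Schedule doses at the last visit, and a site that follows Section 6.5.1.1 does not. Neither rule suits both kinds of woman seen there.

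A woman completing Week 104 on treatment should have her sample taken and then her dose. A woman who attends Early Termination because her drug was stopped should receive nothing. The Schedule column joins the two visits, so a literal reading of the row and footnote w directs a dose to someone whose treatment Section 4.5 has ended. What is at stake is an operational dosing instruction with a patient-safety aspect, and the stated timing of one pharmacodynamic sample. No efficacy estimate is at stake.

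**Working it through.** No arithmetic applies. The check sets the instructions side by side for the two groups of women.

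**Week 104 completers still on treatment**

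| Source | Instruction |
|---|---|
| Table 1-1, in-clinic dosing row | Dose in clinic |
| Footnote w | Last dose in clinic at this visit |
| Section 5.4 | Dose in clinic on this day, not at home |
| Footnote o | Estradiol sample first, then treatment |
| Section 6.5.1.1 | No dose; predose requirement lifted |
| Synopsis, pharmacodynamic endpoint | Change in predose estradiol at Weeks 52 and 104 |

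The first four are consistent with each other and with the endpoint. Section 6.5.1.1 is the outlier: it denies the dose, and it exempts from predose sampling a visit whose endpoint is a predose concentration. For this group, Section 6.5.1.1 is the text to correct.

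**Women at Early Termination whose drug has been stopped**

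| Source | Instruction |
|---|---|
| Table 1-1 row and footnote w | Dose in clinic (combined Week 104/Early Termination column) |
| Section 6.3 | Same procedures as Week 104; exceptions for biopsy and densitometry only |
| Section 4.5 | Treatment ended; attend for the visit's assessments |
| Section 6.5.1.1 | No dose |
| Footnote t | Assumes some women took their last dose well before this visit |
| Section 5.9 | All kits retained by the site at this visit |

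Here Section 6.5.1.1 agrees with Section 4.5, and the row and footnote w are the outliers. The liver-test stop is the clearest case because discontinuation must be immediate. The other safety removals in Section 4.5, such as marked QTcF prolongation, endometrial hyperplasia or bone loss at the withdrawal threshold, raise the same question.

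**Is this only an amendment difference?** No. The row, footnote w and Sections 5.4 and 6.5.1.1 conflict within the current text. The Amendment 2 text in the same file has the same conflict, so it was carried forward.

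**The case against.** The strongest reply is that a stopped woman is already protected by more specific text. Section 4.5 orders the stop and sends her for assessments, and a dose is not an assessment. Pregnancy requires immediate withdrawal under the same section. Section 6.5.1.1 itself says no dose is given at Early Termination. The Schedule's row for dispensing treatment is blank at this visit, and the site keeps the kits. The later version of the protocol breaks off in Section 6.5.2.6, so its Section 7 cannot be read. Its contents list keeps the liver and pregnancy sections, whose Amendment 2 counterparts tell sites to withhold or stop the drug. This reply largely stands as to consequence. It does not remove the contradiction, because the row and footnote w still say otherwise and Section 6.3 lists exceptions without one for dosing.

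Three stronger readings are tempting, and the documents do not support them.

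- *Women stopped for safety would in fact be re-dosed.* The stop rules would normally prevail over a combined column heading.
- *The last-dose date becomes uncertain, which disturbs the Follow-up visit or the biopsy exemption.* The last dose is a recorded fact: the eDiary captures dosing date and time during its collection periods, and the source records hold the drug's end date (Section 10.1.5, Amendment 2 text). Footnote w instructs dosing and does not define the last dose. The "Follow-up visit to assess safety approximately 30 days after the end of study drug treatment" runs from the actual end of treatment, and footnote t likewise depends on when the last dose was taken.
- *The Week 104 estradiol endpoint is compromised.* Under the Schedule the sample precedes the dose; under Section 6.5.1.1 there is no clinic dose that day. The fault is that Section 6.5.1.1 no longer asks for what the endpoint requires.

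**Conclusion.** The contradiction is real and should be corrected, and its impact is low. It concerns at most one dose per woman, at one visit. The row and footnote w are wrong as written for women whose drug has already been stopped. Section 6.5.1.1 is wrong as written for completers still on drug. No effect on the efficacy endpoints, the sample size or the follow-up window is shown. The documents give no rate of safety stops, so the number of women who would meet the conflict cannot be stated.

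The low rating rests on two assumptions: that sites apply Section 4.5 ahead of the Schedule, and that the unseen Section 7 of the later version keeps stop rules like those in Amendment 2. The case for acting is that a dosing instruction should not rely on site judgement to override it, at approximately 320 sites, when a wording change settles the matter.

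**What to change.** 1. In the in-clinic dosing row of Table 1-1 and in footnote w, limit the final clinic dose to women completing Week 104 who are still on treatment.
2. In Section 6.3, add that no study drug is given at Early Termination once treatment has been discontinued.
3. In Section 6.5.1.1, require the Week 104 estradiol sample to be taken predose, and confine the no-dose clause to Early Termination after discontinuation.

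Section 5.4 can stand, since it names only Week 104. Footnote o could usefully say that its order of sample and dose applies when a dose is due.

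The cost is wording in one Schedule row, one or two footnotes and two sections, with no added visits, tests or patients.
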